To compare the two models of nursing care, we will survey all patients directly about the care they receive in the hospital once they are discharged. Surveys tools designed to ascertain medication adherence, disease specific knowledge, as well as satisfaction with care and hospital readmissions will be assessed at 7, 30, and 90 days via follow-up structured telephone interviews. We will consider the 7 day follow-up phone call the baseline assessment. The Morisky scale (MMAS-4),¹⁵ a well validated tool that has been studied in stroke victims,¹⁶ will be used to determine medication adherence. The Stroke Patient Education Retention (SPER)¹⁷ tool will be used to assess patient knowledge. The Stroke Impact Scale (SIS)¹⁸ will be used to evaluate self-perception of stroke deficits by patients. Thirteen other survey questions designed specifically for this study will also be posed to patients at 7, 30 and 90 days from follow up along with two overall quality of life questions at 7 and 90 days. As a secondary outcome, we will calculate and then use a global statistic as a general marker for success to compare the effectiveness of each nursing care model in improving patients' overall outcomes.¹⁹ All interviews will be performed by a trained research assistant who will not be involved in the inpatient care of patients and will be blinded to study allocation. Subject participation will conclude after 90 days.

We will request a waiver of consent for initial enrollment in this study. Follow-up calls to patients will explicitly state according to an IRB-approved script that the questions are part of a research study. Patients will also be asked if they consent to collection of data from their medical record as part of the study. Patients will have the option to participate or decline. If they choose to participate in the interview survey and allow collection of data from their recent hospitalization, then the study will proceed with their verbal consent.

If they decline to participate in the interview survey, then no further study specific tools will be used, but they will be asked if they consent to chart abstraction. However, patients cannot participate in interviews without agreeing to data collection. Patients can decline to participate in both the interviews and allow for data collection. If they fully decline to participate in the study, their data will be expunged and no further data collected.

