3.2 Study Endpoints

3.2.1 Primary Study Endpoints

- Primary endpoints will be stroke education retention as measured by the SPER and medication adherence as measured by MMAS-4 as these are the areas where we anticipate the largest potential effect of the nurse attending. The mean scores on these two tests will be compared between groups at each time interval that they are administered.

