5.5 Subject Compliance Monitoring

Patients will be called at 7, 30, and 90 days following discharge to evaluate their response to the questionnaires. Incomplete response at 7 days will not preclude a phone call directed to patients at 30 and 90 days. Patients who are not reachable via phone interview will not undergo an analysis of their clinical data due to lack of consent.

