6.3 Follow Up Phase of the Study

Follow-up visits will be conducted by telephone only. Informed consent for phone interviews will be obtained prior to the interview. Consent will also be obtained for data collection from the patients Hospital of the University of Pennsylvania electronic medical record. Whether the patient, a family member, or other person is answering the pertinent survey questions will be recorded. Patients may become fatigued when answering the survey questions in which case they can simply ask to stop and the phone conversation will end.

6.3.1 7 days following discharge

At 7 days after hospital discharge, the MMAS-4, SPER, the exploratory 13 Likert-style questions and two modified overall health questions will be administered. There are no well validated surveys regarding the inpatient experience that are patient centered and stroke specific so we designed 13 questions which focus on subject's perception of their inpatient stay as well questions designed to assess quality of life following stroke. The newly devised Likert-style questions as well as the 2 modified overall quality of health questions have been reviewed by a stroke-survivor in her role as patient advocate who was cared for at our institution. The single health literacy question will also be repeated at the 7 day follow up visit and interviewees will be asked about readmission. Though ideally patients will answer all survey questions themselves, responses to survey questions will be accepted from a legal representative provided they can answer accurately. Each interviewee will be identified based on their relationship to the patient on survey collection forms.

6.3.2 30 days following discharge

At 30 days following hospital discharge, the SIS and the MMAS-4 will be administered. Inquiry as to whether or not the patient has been readmitted will occur.

6.3.3 90 days following discharge

At 90 days following hospital discharge, the MMAS-4, SPER, the exploratory 13 Likert-style questions and the 2 modified global quality of health questions will be administered again. Patients will also be asked about any readmissions.

6.4 *Unscheduled Visits*

Clinic visits and other unscheduled visits will not replace phone interviews and will be entirely separate from this study.

6.5 *Subject Withdrawal*

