7.1 Primary Endpoint

The primary endpoint for this study will be a comparison of the mean scores on the SPER and the rate of adherence on the MMAS-4 (score < 2) and the SPER between groups at 7 and again at 90 days.

Scores on the MMAS-4 and SPER will be calculated per protocol. On the MMAS-4, affirmative answers will receive a point and negative answers will be assigned zero. The total score will be the sum of the answer to all four questions. The SPER, question 1 and 2 are scored as follows: 0 = no correct content in response to the question, 1 = the patient provided some but not all of the correct content in response to the question, and 2 = patient provided all key content in response to the question. Question 3-5 were scored as follows as 0 = no correct content in response to the question and 2 = the patient provided the correct response to the questions. A score of 10 indicates all correct responses to the key content.

The SIS is a patient-based, self-report scale in which each item is rated in a 5- point Likert scale in terms of the difficulty the patient has experienced in completing each item. A score of 1 = an inability to complete the item and a score of 5 = no difficulty experienced at all. Using an algorithm, summative scores are generated for each domain.

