7.4 Statistical Methods

In our primary analysis, we will first compare baseline demographics between groups. For our results section, we will compare all patients in the control group to all patients in the intervention arm for outcomes. Mean scores on the SPER will be compared between groups using student t-tests. We will compare proportions of adherent patients on the MMSA-4 between groups using the Pearson chi-square test. Total scores on the SIS, quality of life questions, and the 13 newly devised questions will be compared between groups using t-tests.

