7.5 Subject Population(s) for Analysis

The entire subject population who undergo treatment assignment will be studied primarily via intention to treat analysis comparing data from follow up phone calls between groups. An as-treated analysis will also be performed.

Analysis will be performed on some pre-defined subgroups where we may expect to see effect modification: major stroke vs. minor strokes (NIHSS \leq 5), multiple medications vs. few medications, patients who were admitted following a recurrent stroke vs. a new stroke, and hemorrhagic stroke vs. ischemic stroke subtypes.

8 Safety and Adverse Events

This protocol is extremely low risk as it assigns patients to already existent forms of inpatient care. This study does not include any experimental treatment. Given there is no proposed intervention or proposed management beyond two existing forms of standard clinical care, the routine collection of adverse events is not relevant, as those will be part of routine care. However, there may be a difference between the two arms in terms of specific events of interest. These specific events of interest include falls, aspiration pneumonia, and subsequent (post-discharge) major cardiovascular and cerebrovascular events (MACCE) including stroke (ischemic, hemorrhagic, or unknown), myocardial infarction, and death of any cause. Transfers to a higher level of care (e.g. to the Neuro ICU or medical ICU from the floor) that occur as part of routine care will also be considered events of interest. We will also report any unanticipated events.

All of the aforementioned events of particular interest will be assessed while the subject is in the hospital in keeping with standard clinical care. During follow up phone calls, the interviewee will ask patients and/or their family members specifically about the occurrence of MACCEs including and death of any cause.

The safety of each mode of nursing care while the subject is in-house will be tracked using the quality control processes that are already in place as part of standard inpatient care.

9 Study Administration, Data Handling and Record Keeping

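### SPER and MMAS-4 are measured repeatedly but tested call by call, so early answers from patients missed at day 90 are not used in the day-90 comparison

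*Combined protocol and SAP*

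**What the plan says.** All references are to the combined protocol and SAP.

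- **Collection.** Table 1 and Section 6.3 place SPER at days 7 and 90, and MMAS-4 at days 7, 30 and 90. For day 30, Section 6.3.2 says: "At 30 days following hospital discharge, the SIS and the MMAS-4 will be administered".
- **Comparison times.** Section 3.2.1: "The mean scores on these two tests will be compared between groups at each time interval that they are administered". Section 7.1 names only two times, "and the SPER between groups at 7 and again at 90 days".
- **Tests.** Section 7.4: "Mean scores on the SPER will be compared between groups using student t-tests", and "We will compare proportions of adherent patients on the MMSA-4 between groups using the Pearson chi-square test".
- **Role of day 7.** Section 3.1: "We will consider the 7 day follow-up phone call the baseline assessment". No test in Section 7.4 uses it as a covariate.
- **Incomplete calls.** Section 5.5: "Incomplete response at 7 days will not preclude a phone call directed to patients at 30 and 90 days".
- **Population.** Section 7.5: "The entire subject population who undergo treatment assignment will be studied primarily via intention to treat analysis comparing data from follow up phone calls between" the two arms. It does not say what is done when a call result is missing.

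No mixed model, estimating equation, imputation or other missing-data method appears anywhere. The global statistic in Section 3.2.2 is secondary, combines scales, and is not described as a longitudinal analysis.

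**The concern.** A two-sample test at one call can use only patients with a value at that call. Patients who consented and answered at day 7 (and, for MMAS-4, at day 30) but not at day 90 drop out of the day-90 comparison, although their earlier answers carry information about the missing one. Two things are at stake.

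- **Bias.** The day-90 test needs loss between calls to be unrelated to earlier scores. The protocol makes score-related loss plausible: Section 6.5 lets the investigators discontinue patients for poor adherence to the intervention or study procedures, or because follow-up is hard to obtain, and Section 6.3 lets tired respondents stop. A likelihood-based joint model needs only that loss be explained by the observed scores.
- **Precision.** The joint model recovers part of the information lost with the missing call.

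**Working it through.** **Inputs from the documents (Section 7.3).** 186 per arm; control adherence 65%; improvement of 15%; alpha 0.05; power 80%; SPER SD 2 and difference 0.3.

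**Assumed, because the documents give no figure.** Correlation between day 7 and day 90 (rho) 0.5-0.7; loss after day 7 (d) 25-35%, or 10-40% for power; log-odds of loss rising 0.4-0.8 per SD of lower day-7 SPER.

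**The plan's own figure.** For 65% versus 80%, two-sided 0.05 and 80% power, the usual formula gives 138 per arm (151 with continuity correction), not 186. With 186 per arm the power is 90.3%. For SPER, 186 per arm gives about 30% power at 0.3 points. These are separate matters; here 186 is only the starting number and 0.3 points only a yardstick.

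**1. Precision.** Variance ratio for a day-90 arm mean, joint over separate = 1 - rho² × d.

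| rho | d | Calculation | Ratio | Variance cut |
|---|---|---|---|---|
| 0.5 | 25% | 1 - 0.25 × 0.25 | 0.938 | 6% |
| 0.7 | 25% | 1 - 0.49 × 0.25 | 0.878 | 12% |
| 0.7 | 35% | 1 - 0.49 × 0.35 | 0.829 | 17% |

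Since √0.938 = 0.97 and √0.829 = 0.91, the standard error falls by about 3-9%.

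**2. Power for MMAS-4 at day 90.** Effective n per arm = 186 × (1 - d) / (1 - rho² × d). At d = 30%, 130.2 patients are observed. The joint model is worth 130.2 / 0.925 = 140.8 at rho 0.5 and 130.2 / 0.853 = 152.6 at rho 0.7. Using a continuous-outcome formula for a binary endpoint is an approximation.

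| Missing at day 90 | Separate test | Joint, rho 0.5 | Joint, rho 0.7 |
|---|---|---|---|
| 10% | 87.1% | 87.9% | 88.7% |
| 20% | 82.9% | 84.8% | 86.6% |
| 30% | 77.7% | 80.8% | 83.9% |
| 40% | 71.1% | 75.6% | 80.3% |

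The separate test falls below 80% once more than about 26% are missing (138/186 = 74% needed).

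**3. Bias in SPER at day 90.** With equal SDs at the two calls, the bias in an arm's observed day-90 mean is rho times the amount by which its remaining patients exceed the full arm on day-7 score. The bias in the arm difference is the difference between the two arms' biases, so like mechanisms largely cancel. By simulation:

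| Pattern of loss | Bias (SPER points) |
|---|---|
| Same mechanism in both arms, about 26% control loss, true difference 0.3-0.6 | about 0.01-0.04 |
| Same slope, 20% versus 30% lost | about 0.03-0.10 |
| Score-dependent loss in one arm only, about 26% lost | 0.10-0.28 |

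In the one-arm case the remaining patients exceed the full arm on day-7 score by about 0.20 points (slope 0.4) or 0.40 points (slope 0.8). Multiplying by rho gives 0.10 and 0.20 at rho 0.5, and 0.14 and 0.28 at rho 0.7. Holding loss at exactly 26% gives a maximum of 0.26.

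A separate simulation used a steeper slope (0.5 per point, or 1.0 per SD), about 24% control and 19% attending-nurse loss, and a true difference of 0.6. The day-90 complete-case difference averaged 0.58, 0.57 and 0.55 at rho 0.3, 0.5 and 0.7. The estimate that also used day 7 averaged 0.60 each time.

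**The case against.** The strongest reply is that the loss is modest. Both arms get the same calls, windows and blinded interviewer, so similar dropout is the natural expectation, and bias is then a few hundredths of a point. At 20% missing or less the power gain is small. Section 7.3 calls the trial a pilot project, and call-by-call tests are serviceable if loss is low or similar across arms. This stands, and it limits how much weight the point can bear. It does not remove the point, because the better analysis uses data already collected.

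Three stronger readings might be inferred, and the documents do not support them.

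- **That the day-90 SPER result is off by nearly the 0.3 points in Section 7.3.** This needs score-dependent loss in one arm and none in the other. Differential loss is conceivable, since only one arm forms a relationship with the attending nurse, but nothing in the documents indicates so extreme a pattern.
- **That the day-30 MMAS-4 is left out of the comparisons.** Section 7.1 omits it, but Section 3.2.1 compares scores whenever they are administered. This is an inconsistency between sections.
- **That the trial sets out to test whether a day-7 gain lasts.** Retention is part of the instrument's name. The objective in Section 2.1 is better understanding and adherence under the attending nurse, with no change-over-time aim.

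Two further objections bear on the remedy. A mixed logistic model gives conditional odds ratios, whereas Sections 7.1 and 7.3 are framed as adherence rates. A likelihood-based model would also treat scores after death as ordinary missing values, although Section 8 lists death among the events of interest. Both are met in the fix.

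**Conclusion.** The point holds at moderate weight. Sections 3.2.1, 7.1 and 7.4 test each call separately and no missing-data method is given, so early answers from patients missed at day 90 are unused in the day-90 comparison.

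Under the assumed correlation and loss, the cost in precision is a variance 6-17% lower if a joint model were used. The bias is probably small (about 0.01-0.04 SPER points) if both arms lose patients in the same way, larger (about 0.03-0.10) if the amount of loss differs, and 0.10-0.28 only in the worst case of one-arm selective loss. All sizes rest on assumed dropout, correlation and slope.

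The joint model removes the bias only if loss depends on observed scores; the simulations build that in. Loss driven by a recurrent stroke or readmission need not satisfy it. Nor does the model help patients never reached at any call (Section 5.5), or those whose data are expunged at their request (Section 6.5.1).

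**What to change.** In Sections 7.1 and 7.4, replace the separate tests with one model per endpoint.

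- **SPER:** a mixed model for repeated measures over days 7 and 90, with arm, visit and arm-by-visit terms, unstructured covariance, and all patients with at least one score. Day 7 follows the intervention, so it enters as an outcome and not as a baseline covariate, despite its label in Section 3.1.
- **MMAS-4 < 2:** a likelihood-based mixed logistic model over days 7, 30 and 90 with the same terms. Report model-based marginal adherence proportions by arm and their difference with a 95% confidence interval.
- **Reporting:** arm differences at days 7 and 90 with 95% confidence intervals for both endpoints. Report deaths separately, not as ordinary missing scores.
- **Consistency:** make Section 7.1 agree with Section 3.2.1 on whether the day-30 MMAS-4 is a comparison time.

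The cost is SAP wording and a little more analysis work, with no new data. The downside is reliance on missing at random, which the SAP should state.

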7.2 Secondary Endpoints

The secondary endpoints for this study are the SIS at 30 days, newly devised patient centered outcome survey scales at 7 and 90 days, as well as hospital readmission at 30 days in each group.

The SIS is a patient-based, self-report scale in which each item is rated in a 5- point Likert scale in terms of the difficulty the patient has experienced in completing each item. A score of 1 = an inability to complete the item and a score of 5 = no difficulty experienced at all. Using an algorithm, summative scores are generated for each domain. The SIS is scored in the following way, for each domain:
Transformed Scale = [(Actual raw score - lowest possible raw score) / Possible raw score range] x 100.

The newly devised 13 Likert-questions are all scaled 1 to 5 with 1=strongly disagree and 5 = strongly agree. We have also included two modified global quality of health questions based on the EuroQol instrument where scales range from 1 to 100 and are described in the stem of the question.²⁰ Scores on each set of questions will be added together to compute a total score that can be compared between groups. The overall quality of health questions have scales ranging from 1 to 100 and are described in the stem of the question. Scores on these two questions will be compared between the two groups. These newly devised survey tools were reviewed by a stroke patient representative to assure relevance.

We will likely be underpowered to detect differences in readmission rates between the two groups, given the aforementioned currently low rates of readmission here. However, given the high clinical relevance of readmission we will evaluate this as a secondary outcome in our study.

7.3 Sample Size and Power Determination

For this pilot project, we anticipate that 65% of patients in the control arm will be adherent to medications (MMAS-4 < 2) based on literature reporting 60%¹⁶ adherence as evaluated using these scales in stroke patients and 70%²¹ adherence in patients with hypertension. To achieve success on the primary endpoint, we estimate that patients must improve to by 15% in order to make this intervention worthy of future investigation in a larger study. Assuming an alpha of 0.05 and a power of 80%, with a 1:1 assignment to each arm, we will require 186 patients in each arm for a total of 372 patients. With that number of patients

we will be able to powered to detect a very small difference of 0.3 (delta = .15 (SD=2)) in the mean scores of the SPER based on the published data.¹⁷ Each outcome will be evaluated independently so that we will not need to make any power readjustments. Readmission rates at 30 days are typically low⁴ and likely lower at our institution based on prior data so we will be underpowered for this outcome. Clinically differences on the SIS will depend on the initial stroke severity of patients within each group and therefore the study cannot be powered for this secondary endpoint.

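### The 186 per arm in Section 7.3 does not follow from its stated inputs, so the 80% power for the adherence endpoint is misstated

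*Combined protocol and SAP*

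**What the plan says.** Section 7.3 expects that "65% of patients in the control arm will be adherent to medications", adherence being an MMAS-4 score below 2. The 65% lies between two literature rates, 60% in stroke patients and 70% in hypertension. On the effect to be detected it says "we estimate that patients must improve to by 15% in order to make this intervention worthy of future investigation". The error rates are given as "Assuming an alpha of 0.05 and a power of 80"%, "with a 1:1 assignment to each arm", and the result is that "we will require 186 patients in each arm for a total of 372 patients". The same paragraph rules out any adjustment for having more than one outcome.

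Section 7.4 names the test: "We will compare proportions of adherent patients on the MMSA-4 between groups using the Pearson chi-square test". The Study Summary repeats the total of 372, while Section 4.5 plans 180 per arm. No section states whether the test is one- or two-sided, whether a continuity correction was used, or how many patients are expected to lack the outcome.

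**The concern.** This is the only sample-size calculation in the plan. It sets the total of 372 and supports one of the two primary endpoints. All its inputs stand in one paragraph, so a reader should be able to reproduce 186, and cannot.

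Two things are at stake. First, the wording of the improvement is garbled and can be read as absolute or relative; the required numbers on the two readings differ by a factor of about 2.5 (347/138). Second, the plan does not say whether 186 means patients assigned or patients analysed. That matters here because outcomes exist only for patients who are reached by telephone and consent: Section 5.5 excludes the clinical data of unreachable patients from analysis, and Section 3.1 expunges the data of those who decline fully.

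**Working it through.** **Inputs.** Control rate p1 = 0.65, improvement 15%, alpha 0.05, power 80%, 1:1 (all Section 7.3); uncorrected Pearson chi-square (Section 7.4). Two-sided testing is my assumption; one-sided results are also shown.

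**Formula.** With d = |p2 − p1| and p̄ = (p1 + p2)/2,

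n per arm = [z(1−α/2)·√(2p̄(1−p̄)) + z(power)·√(p1(1−p1) + p2(1−p2))]² / d²

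with z(0.975) = 1.960 and z(0.80) = 0.842. The continuity-corrected size is (n/4)·[1 + √(1 + 4/(n·d))]².

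**Attempt to reproduce 186, absolute reading (65% vs 80%).** p̄ = 0.725 and d = 0.15.
- First term: 1.960 × √(2 × 0.725 × 0.275) = 1.2377.
- Second term: 0.842 × √(0.2275 + 0.1600) = 0.5239.
- n = (1.2377 + 0.5239)² / 0.0225 = 137.9, so **138**.
- Continuity-corrected: 150.95, so **151**.

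**Attempt to reproduce 186, relative reading (65% vs 0.65 × 1.15 = 74.75%).** p̄ = 0.69875 and d = 0.0975.
- n = (1.2717 + 0.5430)² / 0.009506 = 346.4, so **347**.
- Continuity-corrected: 366.6, so **367**.

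**Other variants at 80% power.**

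| Variant | 65% vs 80% | 65% vs 74.75% |
|---|---|---|
| Two-sided, pooled | 138 | 347 |
| Two-sided, continuity-corrected | 151 | 367 |
| Two-sided, unpooled | 136 | 344 |
| One-sided 0.05, pooled | 109 | 273 |
| One-sided 0.05, continuity-corrected | 122 | 293 |

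Starting from the section's two literature rates does not help: a 15-point gain needs 152 per arm from 60% (165 corrected) and 121 from 70% (134 corrected).

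**What would give about 186.** Each of these needs something Section 7.3 does not state:
- 65% vs 80% at 90% power: 184.1, so 185.
- 65% vs 80% at 80% power with a silent loss allowance: 138/0.75 = 184, or 151/0.80 = 188.75, so 189.
- 65% vs 78% at 80% power: 186 unpooled, 189 pooled.

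Which of these produced the figure, if any, cannot be told from the documents.

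**Power at the stated size.** Enumerating both binomial distributions exactly for the uncorrected two-sided chi-square test, with complete outcomes and equal arms:

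| Analysed per arm | 65% vs 80% | 65% vs 74.75% |
|---|---|---|
| 186 (Section 7.3) | 90.4% | 53.7% |
| 180 (Section 4.5) | 89.7% | 52.6% |
| 138 | 80.3% | – |

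**Size of the discrepancy.** On the absolute reading, 186/138 = 1.35, so the stated number is 35% above requirement (186/151 = 1.23, or 23%, against the corrected formula). On the relative reading, 186/347 = 0.54, so it is 46% below.

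**Loss that 186 can absorb on the absolute reading.** 138/186 = 74%, so about 25% of each arm may lack the outcome before power falls below 80%. If 180 is the true target, 138/180 = 77%, so about 23%.

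**The case against.** The best defence is that the error is on the safe side. The paragraph deals throughout in adherence percentages, so a 15% improvement most naturally means 65% to 80%. The number itself points the same way: 186 is close to what ordinary, unstated choices such as 90% power or a 20–25% loss allowance would give for 65% vs 80%, whereas no variant of the relative reading comes near it. On that view the adherence comparison has more than its stated power, and neither the test nor the endpoint is affected.

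Much of this stands. The absolute reading is the likelier one, and the 54% should be read as conditional on the other. It is also fair that 90.4% and 53.7% are nominal: they assume equal arms and complete outcomes. Section 5.2 diverts even-day patients to routine care once the attending nurse has eight patients, so 1:1 is not assured.

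The objection does not rescue the calculation. The stated 80% is wrong on either reading, the text does not settle which reading applies, and a loss allowance that is nowhere written cannot be relied on when follow-up is judged.

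**Conclusion.** The point holds. From 65%, 15%, alpha 0.05, 80% power and 1:1 assignment, the planned test needs 138 per arm (151 corrected) or 347 per arm, not 186, and no standard variant of the stated inputs closes the gap. Nominal power at 186 per arm is about 90% if 15% is absolute and about 54% if it is relative. These figures assume a two-sided test, equal arms and an outcome for every patient.

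On the likelier, absolute reading the trial is not short of patients before losses; what is wrong is the stated power and the missing account of how many analysable patients are needed. Because the figure is the sole basis for the size of the trial and concerns a primary endpoint, it must be corrected.

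**What to change.** Rewrite the adherence part of Section 7.3. If the absolute reading is meant, it could run: the target is a gain of 15 percentage points, from 65% to 80%; 138 analysable patients per arm give 80% power with a two-sided chi-square test at 0.05 (151 with continuity correction); 186 assigned per arm give 90% power if all have the outcome, and at least 80% if no more than 25% in each arm lack it at the time point analysed.

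If 15% relative was meant, withdraw the 80% claim and state about 54%. Keeping 80% power for that effect would need 347 analysable patients per arm.

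In the same edit, settle whether the target is 186 (Section 7.3) or 180 (Section 4.5), and say whether it counts patients assigned or analysed. If it is 180, the tolerable loss on the absolute reading is about 23%.

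The cost is the wording of one paragraph plus the matching number in Section 4.5. The absolute reading needs no extra patients. The relative reading needs none if the lower power is stated openly.

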4.5 Total Number of Patients and Sites

The Hospital of the University of Pennsylvania will be our only enrollment site. We plan to enroll 180 patients in each arm of the trial. At this site, there are approximately 700-800 stroke patients admitted per year, so we anticipate recruitment will require approximately 7 months.

4.6 Vulnerable Populations:

Children, pregnant women, fetuses, neonates, or prisoners are not included in this research study.

5 Study Intervention (Study drug, device, biologic, vaccine, food etc.)

There is no investigational product for this trial as it is a comparative effectiveness study designed to determine whether an attending nurse or standard nursing care improves outcomes for stroke patients. .

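### Section 7.3 claims power for a 0.3-point SPER difference at SD 2, but 186 per arm gives about 30% power for it; the difference detectable with 80% power is 0.58 points

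*Combined protocol and SAP*

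**What the plan says.** Section 3.2.1 names two primary endpoints: "Primary endpoints will be stroke education retention as measured by the SPER and medication adherence as measured by MMAS-4". Section 7.4 gives the tests. For SPER: "Mean scores on the SPER will be compared between groups using student t-tests". For adherence: "We will compare proportions of adherent patients on the MMSA-4 between groups using the Pearson chi-square test".

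Section 7.3 sizes the study on adherence, with 65% adherent in the control arm. The target is worded "we estimate that patients must improve to by 15% in order to make this intervention worthy". The calculation reads "Assuming an alpha of 0.05 and a power of 80%, with a 1:1 assignment to each arm", and concludes that "we will require 186 patients in each arm for a total of 372 patients". The next sentence carries that number over to SPER and says the study is "powered to detect a very small difference of 0.3 (delta = .15 (SD=2)) in the mean scores of the SPER". Alpha is not said to be one- or two-sided.

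Section 4.5 gives a different enrolment figure: "We plan to enroll 180 patients in each arm of the trial".

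**The concern.** The SPER sentence supplies everything needed to check it, and it is explicit about units: 0.3 points divided by an SD of 2 is the printed delta of .15. A standardized difference of 0.15 is small, and 186 per arm is far too few to detect it with the usual power.

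This sentence is the only power justification for a primary endpoint. The protocol concedes that it is underpowered for readmission and cannot be powered for the SIS, so a reader will take SPER to be well covered. A null SPER result could then be read as ruling out even a 0.3-point effect, when a true effect of that size would be missed about 70% of the time.

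The MMAS-4 calculation raises a lesser question, because 186 does not come out of the inputs given for it.

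**Working it through.** **Inputs.** Section 7.3: difference 0.3, SD 2, n = 186 per arm, alpha 0.05, power 80%, 1:1; control adherence 65%, improvement 15%. Section 7.4: two-sample t-test and Pearson chi-square. Section 4.5: n = 180 per arm. Two-sided alpha is my assumption; one-sided results are also shown. The 80% is not repeated in the SPER sentence, and I carry it over from the sentence before. All enrolled patients are taken as analysed.

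**SPER: the plan's figure first**

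- Standardized difference: 0.3/2 = 0.15, as printed.
- Standard error: 2 × √(2/186) = 0.2074.
- Expected test statistic: 0.3/0.2074 = 1.447, against a critical value of 1.966 (370 df).
- Power: normal approximation Φ(1.447 − 1.960) = 0.304; noncentral t 0.303.

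The plan's figure is not reproduced.

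**SPER: what the sample can detect**

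- Difference at 80% power: (1.960 + 0.8416) × 0.2074 = 0.581; by noncentral t 0.583 points (0.2913 SD). 0.583/0.3 = 1.9.
- n per arm for 0.3 points: 2 × (2.8016/0.15)² = 697.7, so 698; by noncentral t 699.
- SD at which 0.3 points would have 80% power: 0.3/0.2913 = 1.03.
- Observed difference of exactly 0.3: p = 0.149. The 95% CI half-width is 1.966 × 0.2074 = 0.408, giving −0.11 to 0.71.

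| Case (SD 2, noncentral t) | Power for 0.3 | 80%-detectable difference |
|---|---|---|
| 186 per arm, two-sided | 30% | 0.58 |
| 186 per arm, one-sided | 42% | 0.52 |
| 180 per arm, two-sided | 29% | 0.59 |
| 372 per arm, two-sided | 53% | 0.41 |

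One-sided, 0.3 points would need 551 per arm.

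**MMAS-4: the 186**

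Formula: n = [1.960√(2p̄(1−p̄)) + z√(p₁(1−p₁) + p₂(1−p₂))]² / (p₂−p₁)².

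- Absolute reading, 65% to 80%, p̄ = 0.725, 80% power: (1.960 × 0.6315 + 0.8416 × 0.6225)² / 0.15² = 137.9, so 138 per arm; 151 with continuity correction.
- Same reading at 90% power: 184.1, so 185 per arm. Power at 186 is 90%; at 180 it is 89%.
- Relative reading, 65% × 1.15 = 74.75%: 347 per arm at 80% power. Power at 186 is 54%.
- Loss that 186 could absorb on the absolute reading: 1 − 138/186 = 26%, or 1 − 151/186 = 19% with the correction.

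No version that keeps the stated 80% power without an allowance for loss gives 186.

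**The case against.** The strongest reply is that this is a slip of units. If 0.3 was meant as a standardized effect (0.6 points at SD 2), power at 186 per arm is 82%, and the detectable effect of 0.29 SD is almost the printed 0.3. That is plausible, and the documents do not settle the cause. But the text prints delta .15 and SD 2 beside the 0.3, so the sentence is wrong as it stands even if this is its origin.

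It can also be said that MMAS-4, not SPER, drove the sample size, that Section 7.3 calls the study a pilot, and that correcting the sentence changes nothing in conduct. All true. It does not excuse a false power statement for a primary endpoint, and Section 3.1 calls the study phase III.

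One objection improves the fix. If 186 includes an allowance for loss, it is a number enrolled. With 138 to 151 analysed per arm, the detectable SPER difference is 0.68 to 0.65 points and power for 0.3 is 24% to 25%. Loss is likely, since interviews depend on reaching patients after discharge and on their consent.

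The MMAS-4 and 180/186 points show no shortfall on the natural, absolute reading. They are matters of disclosure and consistency.

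**Conclusion.** The concern holds. On the printed inputs, power for a 0.3-point SPER difference is 30%, not 80%, and the detectable difference is 0.58 points. This rests on SD 2, 186 analysed per arm, a two-sided 5% t-test and the 80% carried over from the preceding sentence. Dropping two-sidedness (42%, 0.52 points) or using 180 per arm (29%, 0.59 points) does not rescue the claim, and loss to follow-up makes it worse. Because it concerns a primary endpoint, it must be fixed.

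The basis of 186 for MMAS-4 is undisclosed: conservative if the 15% is absolute (90% power), inadequate if relative (54%). The difference between 180 and 186 is minor.

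**What to change.** 1. Replace the SPER sentence in Section 7.3 with: *With 186 analysed per arm and SD 2, the study has 80% power (two-sided alpha 0.05) for a SPER difference of 0.58 points; power for 0.3 points is about 30%.* Drop the description of the difference as very small. If 186 is the number enrolled, give the detectable difference for the number expected to be analysed. The sponsor should confirm whether 0.3 was meant in points or in SD units.
2. For MMAS-4, state whether 15% is absolute or relative, the power that 186 gives on that reading, and any allowance for non-response.
3. Make Sections 4.5 and 7.3 agree on the number per arm.

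The cost is wording and a less favourable SPER figure. Enrolment and analyses can stay as they are. If the sponsor confirms a relative 15%, it must also report 54% power for MMAS-4.
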